8.2 Adverse Event Reporting

All adverse events occurring from the informed consent signature until 30 calendar days after last study drug (pracinostat/placebo) intake, or until the initiation of new therapy for AML, whichever occurs first, are to be recorded on the appropriate eCRF section.

Every effort must be made by the Investigator to categorize each adverse event according to its severity and its relationship to the study treatment (study drug and/or azacitidine).

All AEs will be followed until symptom resolution or until the condition stabilizes, unless, in the Investigator's opinion, the AE or laboratory abnormality/ies are not likely to improve because of the underlying disease or unless the patient is lost to follow-up.

Whenever a change in the severity of an AE (such as a worsening) has occurred, a follow up of the initial AE should be entered in the eCRF reporting the new severity.

Outcome of ongoing serious and non-serious AEs will be reported in eCRF until the end of the reporting period as above defined. All non-resolved serious and non-serious AEs beyond such date will be recorded in eCRF as "ongoing" without further follow-up.

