8.2.1 Serious Adverse Event (SAE)

Any SAE, irrespective of the relationship to study treatment, must be reported by the Investigator to CRO. Within 24 hours of the study site staff becoming aware of any SAE, the Investigator or the Investigator's designee must complete the eCRF with all necessary information. Any accompanying source documents (hospital records, autopsy report, etc.) should be faxed or e-mailed (as PDFs) at the following 24-hours contact information:

Email: [contact]

[contact]

SAEs should be collected from the informed consent signature until 30 calendar days after discontinuation or completion of study treatment, or until the initiation of new therapy for AML, whichever occurs first, and followed until resolution.

"Disease progression" or "relapse from remission" as such, should not be reported as SAEs.

"Death" is an outcome and should not be reported as an SAE, unless the cause leading to death is unknown. When recording an SAE with an outcome of death, the event or condition that caused or contributed to the fatal outcome should be recorded as the single serious adverse event term.

The Investigator must immediately (within 24 hours) report follow-up information for initial events to Clinipace and the Sponsor as described above. Follow-up information can include but is not limited to the following significant information:

- New signs or symptoms or a change in the diagnosis
- Clinically significant new diagnostic test results
- Change in causality based on new information
- Change in the event's outcome, including recovery
- Additional narrative information on the clinical course of the event

Investigators must also comply with local requirements for reporting of initial and follow-up SAEs to their Institutional Review Board (IRB)/ Ethics Committee (EC) according to their own interpretations of the regulations and their own institutional policies.

The Sponsor/ designee is responsible for SAE reporting to the Regulatory Authorities where the study is conducted, according to reporting requirements as per local regulatory rules.

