Each TEAE is collected in the eCRF by recording one initial record and one record for each change in seriousness and/or severity within the same occurrence of the event. A summary record will be derived aimed at being used for the production of the summary tables, while individual records will only be listed.

The summary record will pick-up among the collected records relevant to the same event (it is allowed to collect one field from one record and another field from another record) the maximum seriousness and the maximum severity. Actions taken will be picked up from all the records in order to keep all the actions taken with the event. The outcome will be picked up from the last record in time-sequential order. The relationship will be reconciled during data cleaning, so it will be the same in all of the records related to the same event at time of analysis.

As MRD (positive/negative) will be obtained together with the other data related to MRD analyses from the external lab, CR_{MRD} will be derived in the CDISC datasets from CR and MRD results.

Adverse events of special interest (as described in the study protocol) will be retrieved according to the following rules reported in the table:

AESI	MedDRA SMQ (v.20.0)	MedDRA PT (v. 20.0)	Comments
QTc prolongation	Torsade de Pontes/QT prolongation (SMQ) - NARROW	n/a	
Supraventricular arrhythmias	Supraventricular tachyarrhythmias (SMQ) - NARROW	n/a	
Sepsis, septic shock, grade ≥ 3 lung infection (pneumonia), any infection leading to death	Toxic-septic shock conditions (SMQ) - NARROW	1.Any PT that includes the word sepsis 2.Exact match to the PT pneumonia or lung infection	Pneumonia only if grade ≥ 3

Grade ≥ 3 anemia, neutropenia, febrile neutropenia and thrombocytopenia	n/a	
1.Any PT that includes the word anaemia.
 
2.Exact match to any of the following PTs:
 
Haemoglobin decreased Band neutrophil count decreased Band neutrophil percentage decreased Febrile neutropenia Granulocyte count decreased Granulocytopenia Neutropenia Neutropenic infection Neutropenic sepsis Neutropenic colitis Neutrophil count decreased Neutrophil percentage decreased Platelet count decreased Platelet production decreased Thrombocytopenia Febrile bone marrow aplasia
	All listed PTs only if grade ≥ 3
Grade ≥ 3 haemorrhage	n/a	Any PT that includes the word haemorrhage or haematoma or bleeding	All listed PTs only if grade ≥ 3

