9.2.5 Deaths

The number and percentage of deaths will be summarized by treatment and cause. All deaths will be additionally listed together with treatment group, dosing parameters, death date, primary cause of death and autopsy values.

Patients who died within 30 days, 60 day and 90 days from randomization will be additionally summarized.

The number and percentage of patients reporting treatment-emergent SAEs resulting in death will be tabulated by treatment group, System Organ Class (SOC) and Preferred Term (PT) (sorting for SOC and PT in alphabetical order).

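### Protocol 8.2 stops outcome follow-up of unresolved SAEs when the reporting window closes and 8.2.1 does not, so fatal treatment-emergent SAEs may be recorded inconsistently and under-counted

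*Protocol*

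**What the plan says.** **Protocol 8.2** collects AEs from consent "until 30 calendar days after last study drug (pracinostat/placebo) intake, or until the initiation of new therapy for AML, whichever occurs first". On follow-up it begins broadly: "All AEs will be followed until symptom resolution or until the condition stabilizes", with exceptions for events the investigator thinks unlikely to improve because of the underlying disease and for patients lost to follow-up. It then sets a limit: "Outcome of ongoing serious and non-serious AEs will be reported in eCRF until the end of the reporting period as above defined". For whatever is still open at that point: "All non-resolved serious and non-serious AEs beyond such date will be recorded in eCRF as 'ongoing' without further follow-up".

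**Protocol 8.2.1** has its own SAE rule. The collection window is "30 calendar days after discontinuation or completion of study treatment". The sentence then gives the alternative end of the window and the follow-up duty: "or until the initiation of new therapy for AML, whichever occurs first, and followed until resolution". Follow-up information is due within 24 hours, and a change in the event's outcome is one of the listed examples. SAE information is entered in the eCRF.

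**SAP 6.4** builds one summary record per event from the eCRF records. It takes the maximum seriousness and severity. For outcome: "The outcome will be picked up from the last record in time-sequential order".

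**SAP 9.2.2** puts fatal SAEs, and fatal SAEs related to either drug, in the TEAE overview. **SAP 9.2.5** adds: "The number and percentage of patients reporting treatment-emergent SAEs resulting in death will be tabulated by treatment group", by system organ class and preferred term.

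**The concern.** The question is what happens to the outcome of an SAE that began inside the window, not which onsets are collected. Section 8.2 closes the outcome field when the window closes and names serious events in doing so. Section 8.2.1 keeps it open until resolution. A site can defend either practice from the protocol text.

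The tables at stake are the ones that attribute deaths to coded events and to treatment. Pracinostat is being added to azacitidine, and protocol 1.3 reports two Phase II deaths considered related to both drugs, from neutropenic sepsis and febrile neutropenia. Fatal related SAEs are therefore a central safety output. An event still open when the patient moves to another AML therapy is the kind that 8.2 would close early.

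**Working it through.** No arithmetic applies, and the plan gives no figure to reproduce. The check is a comparison of the texts, followed by one case traced through them.

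**1. Do the two protocol rules conflict?**

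| | Protocol 8.2 | Protocol 8.2.1 |
|---|---|---|
| Events covered | Serious and non-serious AEs | SAEs |
| Outcome updated until | End of the reporting period | Resolution |
| Unresolved at window close | Marked ongoing, no more follow-up | Still followed; change of outcome reportable |
| Where recorded | eCRF | eCRF |

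They conflict for any SAE unresolved when the window closes. The 8.2 rule cannot be read as applying to non-serious AEs only, because it names serious ones.

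**2. Is such an event treatment-emergent?** Yes. Protocol 8.1.1.5 and SAP 9.2.2 define treatment emergence by onset or worsening within the window. The date of death plays no part.

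**3. Which record decides whether it is fatal?** SAP 6.4 uses the last eCRF record. The SAP states no reconciliation with the death record or with a safety database.

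**4. Could the death enter as its own event?** Not normally. Protocol 8.2.1 treats death as an outcome and allows it as an SAE term only when the cause is unknown. The fatal outcome has to sit on the record of the causing event.

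**5. Trace one illustrative case.** An SAE starts on day 25 after the last capsule, new AML therapy starts on day 27, and the patient dies of the SAE on day 33.
- The 8.2 window closes at the earlier of day 30 and day 27, which is day 27.
- Site following 8.2: the outcome stays ongoing, and the event is not in the fatal-SAE tables.
- Site following 8.2.1: the outcome is updated to fatal on day 33, and the event is in the tables.

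**6. Does another planned contact recover the outcome?**
- The End of Treatment visit (protocol 5.1.14) takes place about 30 days after treatment ends, or before new treatment starts, so it falls at about the time the window closes.
- In-study long-term follow-up (protocol 5.2) collects new AML treatment, progression and survival status, but not SAE outcome.
- Post-study follow-up (protocol 5.3) collects follow-up of serious adverse reactions, but only after the end of the study and only for related events.

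**7. What is kept in any case?** OS counts every death. SAP 9.2.5 summarises deaths by treatment and cause, gives deaths within 30, 60 and 90 days of randomization, and lists death date and primary cause.

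**The case against.** The best defence is that 8.2.1 is the SAE-specific rule and so governs SAEs, while 8.2 only limits routine eCRF entry. Part of this stands: sites that give 8.2.1 precedence will update the outcome, so loss is not certain. It does not remove the conflict, because 8.2 names serious AEs, rules out further follow-up, and concerns the same eCRF that 8.2.1 uses.

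Four stronger readings are tempting, and the documents do not support them.

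- *That late-fatal SAEs necessarily drop out of the tables.* They do so only where 8.2 is applied over 8.2.1.
- *That Grade 5 is also lost.* This is not settled. Section 8.2 separately asks for a new record whenever severity changes and puts no cut-off on that sentence, and SAP 6.4 takes the maximum severity. A site might enter the worsening to Grade 5 even after the window.
- *That the size can be put at a few events.* A reader might scale the Phase II rate, 2/50 = 4%, to 4% × 250 = 10 related deaths in the pracinostat group and assume that some share came late. Nothing says that either Phase II death fell after a reporting cut-off, and no document supports any late share.
- *That the SAP wrongly excludes deaths after the window.* It does not. Treatment emergence already rests on onset or worsening, and SAP 9.2.5 sets no limit on the date of death. The gap is in data collection and in the missing check against the death record.

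**Conclusion.** The inconsistency is real and should be resolved. For an SAE with onset in the window and a fatal outcome after it, protocol 8.2 and 8.2.1 lead to different last records. SAP 6.4 carries that difference into the fatal-SAE row of the overview, the related fatal-SAE row and the table of SAEs resulting in death. Fatal treatment-emergent SAEs may therefore be recorded inconsistently between sites and under-counted overall.

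The size cannot be estimated: the documents give neither the number of SAEs open when the window closes nor the number fatal afterwards. The conclusion assumes only that some sites will apply 8.2 as written.

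The primary endpoint is not affected, and no death disappears from the report. What may be lost is the attribution of a death to a coded event and to study drug or azacitidine.

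**What to change.** 1. **Protocol 8.2 and 8.2.1.** Limit the rule that leaves events as ongoing to non-serious AEs. State that for any SAE with onset in the window, the outcome, and any worsening to Grade 5, is updated in the eCRF to resolution, stabilisation or death, including after the window closes or new AML therapy starts. In the same edit, align the start of the 30 days: 8.2 counts from the last capsule, while 8.2.1 counts from the end of study treatment, which by protocol 3.1 includes azacitidine.
2. **Protocol 5.2.** Add the outcome of unresolved SAEs to the items collected at the 3-monthly contacts. Those contacts do not collect it now.
3. **SAP 6.4 and 9.2.5.** Before the fatal-SAE tables are produced, check every treatment-emergent SAE left as ongoing in a patient who died against the recorded death date and primary cause, in the same way in both groups, and query the site where they match. The death listing already holds both fields, so this step can be taken even late in the study.

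The cost is a short protocol edit, one added follow-up item with its eCRF field, some extra entries and queries, and a possibly slightly higher fatal-SAE count.

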8.2.1 Serious Adverse Event (SAE)

Any SAE, irrespective of the relationship to study treatment, must be reported by the Investigator to CRO. Within 24 hours of the study site staff becoming aware of any SAE, the Investigator or the Investigator's designee must complete the eCRF with all necessary information. Any accompanying source documents (hospital records, autopsy report, etc.) should be faxed or e-mailed (as PDFs) at the following 24-hours contact information:

Email: [contact]

[contact]

SAEs should be collected from the informed consent signature until 30 calendar days after discontinuation or completion of study treatment, or until the initiation of new therapy for AML, whichever occurs first, and followed until resolution.

"Disease progression" or "relapse from remission" as such, should not be reported as SAEs.

"Death" is an outcome and should not be reported as an SAE, unless the cause leading to death is unknown. When recording an SAE with an outcome of death, the event or condition that caused or contributed to the fatal outcome should be recorded as the single serious adverse event term.

The Investigator must immediately (within 24 hours) report follow-up information for initial events to Clinipace and the Sponsor as described above. Follow-up information can include but is not limited to the following significant information:

- New signs or symptoms or a change in the diagnosis
- Clinically significant new diagnostic test results
- Change in causality based on new information
- Change in the event's outcome, including recovery
- Additional narrative information on the clinical course of the event

Investigators must also comply with local requirements for reporting of initial and follow-up SAEs to their Institutional Review Board (IRB)/ Ethics Committee (EC) according to their own interpretations of the regulations and their own institutional policies.

The Sponsor/ designee is responsible for SAE reporting to the Regulatory Authorities where the study is conducted, according to reporting requirements as per local regulatory rules.

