3 STUDY PLAN

3.1 Study Design

This is a Phase III, double-blind, placebo-controlled, multicenter, randomized study of pracinostat in combination with azacitidine (AZA) in patients ≥ 18 years of age with newly diagnosed acute myeloid leukemia (AML) not fit to receive intensive induction chemotherapy.

A maximum of 500 patients are planned to be enrolled over a period of approximately 30 months at approximately 130 study centers. Patients who meet the eligibility criteria and consent to participate will be randomized 1:1 to Group A (experimental group) or Group B (control group). Randomization will be stratified by cytogenetic risk category (intermediate vs. unfavorable risk) and ECOG Performance Status (0-1 vs. 2).

Study treatment, defined as the treatment with pracinostat/placebo (study drug) in addition to the background therapy (AZA), will continue until there is documented disease progression or relapse from CR while receiving study treatment, or non-manageable toxicity. There is no upper limit to the number of treatment cycles administered, and study treatment should be continued as long as patients derive a clinical benefit.

In the Phase II study MEI-004, 6 patients (12%) required more than 6 cycles of pracinostat + AZA to achieve a CR. It is recommended, therefore, that patients who have no evidence of disease progression should receive a minimum of 6 cycles of study treatment to allow adequate exposure to study drug and background therapy before considering a switch to other therapies.

[figure not shown]
Once permanently discontinued from study treatment, patients will be followed for AEs (for 30 days) and then they will enter the Long-term Follow-up phase of the study (Section 5.2). Patients in the Long-term Follow-up phase of the study will be followed every 3 months (± 1 month) for documentation of disease progression, if applicable, and overall survival. Patients will be followed until death or until end of this study (refer to Section 3.2 for end of this study definition).

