4.5.1 Dose Modification or Interruption for Hematologic Toxicity

Dose modification for hematologic toxicity in the setting of AML is not allowed during the first cycle of treatment (Cycle 1) and not recommended in general, unless the patient is in remission as dose delays and/or reductions may decrease exposure to therapeutically effective levels of drugs.

[figure not shown]
Since myelosuppression (i.e., thrombocytopenia, anemia, leukopenia, and neutropenia) has been reported with similar frequency with pracinostat and AZA therapy, the AZA dose should be reduced first.

From cycle 2 onwards the following criteria are recommended:

- a) **Subjects with baseline ANC <1,500 cells/ μ L or platelets <75,000 cells/ μ L and have a \geq Grade 3 decrease in cell counts before starting next treatment cycle:**

 1. $\leq 50\%$ decrease: may continue treatment with no delay or dose adjustment.
 2. **>50% decrease and a bone marrow evaluation is not required per study protocol:** delay treatment. If recovery is achieved within 14 days, no dose adjustment is required. If recovery is not achieved within 14 days, at day 42 a bone marrow evaluation is suggested and dose adjustment is outlined in [Figure 2](#).
 3. **>50% decrease and a bone marrow evaluation is required per study protocol:** follow dose adjustment outlined in [Figure 2](#).

Figure 2: Dose Adjustment

*Recovery= count \geq nadir count + [0.5 x (baseline count – nadir count)]

b) **Subjects without reduced baseline counts (ANC \geq 1,500 cells/ μ L and platelets \geq 75,000 cells/ μ L) and have a \geq Grade 3 decrease in cell counts before starting next treatment cycle: delay treatment. If recovery is achieved within 14 days, no dose adjustment is required. If recovery is not achieved within 14 days the dose should be adjusted as follows:**

1. **ANC $>$ 1.000 cells/ μ L and PLT $>$ 50.000 cells/ μ L:** no dose adjustment is required;
2. **ANC \leq 1.000 cells/ μ L and/or PLT \leq 50.000 cells/ μ L:** consider reduction of AZA to dose level -1.

If it is determined that further dose modifications are still required after two AZA dose reductions, then pracinostat dose should be reduced. Unless a patient achieves $<$ 5% blasts in the bone marrow, a cycle should not be interrupted beyond 28 days due to hematologic toxicity.

Patients with drug interruptions for prolonged myelosuppression (defined as $>$ 56 days [2 cycles] with ANC $<$ 500/ mm^3 or platelet count $<$ 10.000/ mm^3 in a bone marrow with $<$

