5.2 In-Study Long-term Follow-Up

After patients permanently discontinue pracinostat/azacitidine or placebo/azacitidine, they will be followed every 3 months (± 1 month) from the date when study drug was last administered until the end of the study. The following information will be obtained during these Follow-up contacts:

- Collect any new AML treatment
- Collect any evidence of disease progression
- Assess survival status

- When there is a suspicion of disease progression, a bone marrow evaluation is required to confirm disease progression

Every effort must be made to follow patients from the time of treatment discontinuation until death. Patients may be contacted during outpatient visits or by telephone.

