5.3.1 Patients on treatment at the end of study

For patients still on treatment at the end of study the following information will be collected in a dedicated CRF:

- End of treatment (date of last study drug administration)
- Any new AML treatment
- Any evidence of disease progression
- Serious Adverse Reactions (SARs) and follow-up information of SARs
- Death

5.3.2 After discontinuation of the treatment each patient enters in the post-study long-term follow-up as described below. Post-study long-term follow-up

After the end of the study, patients on post-study long-term follow-up will continue to be followed every 3 months (± 1 month). The following information will be obtained during these Follow-up contacts and recorded in a dedicated CRF:

- Any new AML treatment
- Any evidence of disease progression
- Survival status
- Serious Adverse Reactions (SARs) and follow-up information of SARs

Every effort must be made to follow patients from the end of the study until Death. Patients may be contacted during outpatient visits or by telephone.

Results of this post-study observation period will be described in a separate study report.

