9.2.1 Pre- and post-study adverse events

Pre-treatment AEs and post-treatment AEs (if any) will be listed.

Pre-treatment AEs are defined as adverse events starting before the first dose of pracinostat/placebo is given, and which did not worsen during treatment period.

Post-treatment AEs are defined as adverse events starting after the end of the observation period, which is defined as 30 days after the last dose of pracinostat/placebo, or start of a new therapy for AML, whichever occurs first.

However, to avoid missing important AEs, also AEs started within 30 days after last dose of pracinostat/placebo after start of a new therapy for AML will be considered as post-treatment events but will be flagged within the related listing.

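### New-onset related SAEs after the 30-day or new-therapy cut-off are not asked for while the study runs, although follow-up contacts at the same interval ask for them once it has ended

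*Protocol*

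**What the plan says.** **Cut-off.** Protocol 8.2 records adverse events "until 30 calendar days after last study drug (pracinostat/placebo) intake, or until the initiation of new therapy for AML, whichever occurs first". Section 8.2.1 sets the SAE limit at "30 calendar days after discontinuation or completion of study treatment, or until the initiation of new therapy for AML, whichever occurs first". Footnote U of the Schedule of Assessments repeats the stop. None of the three makes an exception for events the Investigator considers related.

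**In-study follow-up.** Section 3.1 gives the order of phases: "patients will be followed for AEs (for 30 days) and then they will enter the Long-term Follow-up phase of the study". Under 5.2, "they will be followed every 3 months (± 1 month) from the date when study drug was last administered until the end of the study". The items at these contacts are new AML treatment, progression ("Collect any evidence of disease progression"), survival status, and a marrow if progression is suspected. Footnote V lists the same items, and the follow-up column of the schedule has no adverse-event mark.

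**Post-study follow-up.** Section 5.3.2 keeps the 3-monthly interval and the three core items, and adds "Serious Adverse Reactions (SARs) and follow-up information of SARs". The same item appears in 5.3.1 for patients still on treatment.

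**SAP.** Section 9.2.1 treats as post-treatment, and flags in the listing, a particular group of events: "to avoid missing important AEs, also AEs started within 30 days after last dose of pracinostat/placebo after start of a new therapy for AML". Section 9.2 lists all AEs whenever they were reported.

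**The concern.** The sponsor has judged it worthwhile and feasible to ask about serious adverse reactions at 3-monthly off-treatment contacts, but does so only after the 390th death. No reason is given for leaving the item out while the study runs.

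What is at stake is the completeness of the safety comparison. Patients who stop for toxicity that cannot be managed (7.1) are an obvious group in whom a late related event might begin. The new-therapy limb can also close the window well before day 30, since 5.1.14 allows the end-of-treatment evaluation to be brought forward when new treatment is urgent. If the arms differed in the time from last dose to new therapy, the length of capture would differ by arm.

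The SAP adds a smaller mismatch. It plans to flag AEs that follow new therapy within 30 days of the last dose, but Protocol 8.2 and 8.2.1 tell sites to stop recording at that point. The flag can show only what a site enters beyond its instructions.

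**Working it through.** **1. The figure that fixes the end of the study.** The concern rests on no power figure, but it depends on when the post-study period opens. Protocol 9.11 expects 390 deaths at about 30 + 18 = 48 months. A simulation (400 runs) used the plan's inputs: 100 patients in year 1, 400 over the next 18 months, median OS 10 and 14 months with exponential survival, and 3% yearly drop-out. It gives a mean of 47.3 months, so the plan's timeline is reproduced.

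**2. One event, two periods.** Take a related SAE beginning 45 days after the last dose.
- *Study still running:* day 45 is past the 30-day limit in 8.2 and 8.2.1, so no report is required. The first 5.2 contact falls 2 to 4 months after the last dose (3 ± 1) and has no item that would elicit it.
- *After study end:* the patient is in 5.3.2 follow-up at the same interval, and the serious-adverse-reaction item asks for it.

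**3. Could other text close the gap?**
- Section 8.2.1 opens by requiring any SAE to be reported whatever its relationship, but the collection window in the same section limits that duty.
- SAP 9.2 and 9.2.1 list post-treatment AEs if there are any. A listing creates no duty to collect.
- SAP 9.2.5 summarises deaths by treatment and cause. That covers fatal events in part and non-fatal ones not at all.
- SAP 9.2.4 tabulates only treatment-emergent and drug-related SAEs, in the format of 9.2.2, whose observation period ends at the same cut-off.

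**4. Reach of the post-study contacts.** Assume 500 patients are enrolled.
- Dead at study end: 390/500 = 78%.
- Ceiling on patients reaching the post-study period: 500 − 390 = 110, and 110/500 = 22%.
- After drop-out in the simulation: about 93 patients, 93/500 = 19%.

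This is the reach of the only contacts that ask. It is not a count of missed events.

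**5. How many patients live past the window?** The documents do not say, so this needs an assumption. With constant hazards of death and discontinuation, median OS m and mean treatment time d (months), λ = ln 2 / m. The share leaving treatment alive is 1 − λd, and the share alive one month later is (1 − λd)·exp(−λ).
- m = 10, d = 8 (the average in 3.1): λ = 0.0693; 1 − 0.5545 = 0.4455; × 0.933 = 0.416.
- m = 14, d = 8: λ = 0.0495; 1 − 0.3961 = 0.6039; × 0.952 = 0.575.
- With d from 5 to 9 months, the range is 35% (m = 10, d = 9) to 72% (m = 14, d = 5).

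These patients would have some time outside the window. The calculation says nothing about how many would have a related SAE in that time.

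**6. Two further mismatches between 8.2 and 8.2.1.**
- *Follow-up:* 8.2 leaves unresolved serious and non-serious events as ongoing, with no further follow-up once the reporting period ends. 8.2.1 has SAEs followed to resolution.
- *Clock:* 8.2 counts from the last pracinostat/placebo intake. 8.2.1 counts from the end of study treatment, which by 3.1 includes azacitidine.

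**The case against.** A fixed window is a legitimate design choice. This one recurs in the protocol and in SAP 9.2.1 and 9.2.2, is identical in both arms, matches the TEAE definition in SAP 9.2.2, and avoids attributing events after a new AML therapy, when causality is hard to judge. That explains the TEAE window. It does not explain why related SAEs are asked for at off-treatment contacts only after study end.

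The objection does narrow the point. A reader might draw five stronger conclusions that the documents do not support.

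- **That prolonged toxicity in general is lost.** Under 8.2.1, an SAE with onset inside the window is followed to resolution, subject to the conflict with 8.2. Only new onset after the window is affected.
- **That the 56-day myelosuppression rule in 4.5.1 shows the window is too short.** That rule concerns patients whose drug is interrupted and who may restart. They have not discontinued, so the 8.2.1 clock has not begun.
- **That capture is looser in the main study than afterwards.** On treatment the reverse holds: the main study records every AE and SAE, whereas 5.3.1 collects only serious adverse reactions. The asymmetry is confined to off-treatment contacts.
- **That a late event can never appear as a related SAE by arm.** If a site enters it, the SAP lists it with relationship, sorted by treatment group. It is unsolicited and not tabulated, rather than impossible to see.
- **That the averages in 3.1 measure the harm.** They give 8 + 28/30.4375 + 6 = 14.92 months, 6/14.92 = 40% of time, and 500 × 6/12 = 250 patient-years. This is follow-up time, including time far from the last dose and time on other therapy. Section 3.1 does not say whether the 6-month average covers everyone or only those who enter follow-up.

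**Conclusion.** The point holds in a limited form. While the study runs, a related SAE with onset after the earlier of 30 days and new AML therapy is neither required nor solicited from patients off treatment. After study end, contacts at the same interval solicit it. Nothing in the protocol or SAP removes this asymmetry.

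At most 110 of 500 patients (22%) can reach the contacts that ask, assuming 500 are enrolled and the study ends at 390 deaths. Section 5.3.2 does not say whether those contacts look back to events that began before study end. It would be tempting to conclude that late related toxicity goes unrecorded for most patients. The documents do not support this: they do not give the number of patients with such an event, and the share alive beyond the window is itself uncertain (35% to 72% under the stated assumptions).

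This is an inexpensive improvement to safety data. The primary OS analysis, the 390-event target, the one-sided alpha of 0.025 and power are all unaffected.

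**What to change.** - **Protocol 8.2.1** (with 8.2 and footnote U aligned): add that after the window, and regardless of new AML therapy, any SAE the Investigator considers related to pracinostat/placebo or azacitidine is reported until the end of the study.
- **Protocol 5.2 and footnote V:** add "Serious Adverse Reactions (SARs) and follow-up information of SARs", as in 5.3.2.
- **SAP 9.2.1 and 9.2.4:** tabulate these post-treatment related SAEs by arm, separately from TEAEs, and flag whether onset was before or after new AML therapy. Align the existing flag for events after new therapy with what sites are told to record.
- **Protocol 8.2 and 8.2.1:** reconcile the two statements on follow-up of unresolved SAEs and the two starting points of the 30-day clock.

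The cost is one item at contacts that already take place, one table, and some extra SAE reports whose causality is less certain after a new therapy.

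SAP section 11 says that version 5 reflects decisions taken after the interim results were unblinded, so in-study follow-up may be largely over. In that case, tabulate by arm the late related SAEs that were recorded, and state in the study report that such events were not solicited during in-study follow-up.
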